5.2 Schematic diagram of the experimental plan

The schematic diagram of the study is shown below.

	Screening	Baseline		
Visit	T0	T1	T2	T3
Months		\pm 7-15 days after T0	6 months after T0	12 months after T0
Time window			\pm 10 days	\pm 10 days
Informed consent	✓			
Demographic data	✓	✓		
Medical records	✓	✓		
Visual Field	✓	✓	✓	✓
PERG	✓	✓	✓	✓
PEV	✓	✓	✓	✓
OCT	✓	✓	✓	✓
Concomitant diseases	✓	✓	✓	✓
Previous treatments	✓	✓		
Concomitant treatments	✓	✓	✓	✓
Complete Ophthalmological examination: visual acuity anterior and posterior biomicroscopy ophthalmoscopy intraocular pressure	✓	✓	✓	✓
Magnetic Resonance		✓		✓
Inclusion/exclusion	✓	✓	✓	✓
Randomization		✓		
Compliance			✓	✓
Delivery of food Supplement or Placebo		✓	✓	
Incidents			✓	✓

5.3 Trial term and visits

The study will last a total of 24 months, of which 12 for the selection and enrollment of patients and 12 months of follow-up from the last patient enrolled. During this period, patients will undergo 4 visits:

- T0 screening visit
- baseline visit T1
- visit at 6 months T2
- visit at 12 months T3

5.4 Planned visits

The visits will be performed at T0 (screening), at T1 (baseline, 7-15 days after T0), after 6 months (T2) and after 12 months (T3) of follow-up not knowing which group the subject belongs to.

After screening (T0), enrolled patients will perform a baseline visit (T1) during which they will be randomized to one of the two groups. The visits will take place 6 and 12 months after the baseline visit.

A complete eye examination will be performed at T0, T1, T2 and T3 including the following assessments: corrected visual acuity, biomicroscopy, indirect ophthalmoscopy, intraocular pressure measurement with Goldmann applanation tonometer, CV test, recording of PERGs and VEPs, imaging of the optic nerve and retinal nerve fiber layer by OCT. Neuroradiological evaluation will also be performed at T1 and T3.

At the end of the T1 visit, the patient will be given 4 bottles containing 500 ml Neurotidine® or Placebo and will be given the relative instructions for administration. The regimen will be 1 administration of 10 ml once a day for 6 months. Each bottle can be used for 50 days. At the end of the 6 month period the patient will be asked to hand over the used bottles.

After 6 months \pm 10 days (T2), patients will be given an additional 4 bottles containing Neurotidine® or Placebo and will be given instructions for their administration. The regimen will be 1 administration of 10 ml once a day for 6 months. Each bottle can be used for 50 days. Again at the end of this 6 month period the patient will be asked to hand over the used bottles.

5.5 Outcomes

The nerve conduction along the post-retinal optical pathways will be determined through the evaluation of the RCT through the simultaneous recording of PERG and PEV, the function of the RGCs will be evaluated through the recording of the PERG, the morphological evaluation of the RGCs will be carried out through the OCT evaluations and the morphological and functional evaluation of the nerve structures that form the optical pathways will be performed by means of Cerebral Magnetic Resonance (MRI).

The primary objective is the assessment of changes in the RCT in patients treated with citicoline in oral solution compared to changes in the RCT assessed in patients treated with placebo.

The secondary objectives will be to evaluate whether the changes in RCT in patients treated with Citicoline in oral solution are associated or not with **morphological and functional changes in the nerve structures that form the optical pathways** (NGL, optic tract, visual cortex) and if both conditions may be related to the morpho-functional variations of the RGCs and of the visual field.

5.5.1. Psychophysical Evaluations

a) Visual Field (VF)

Static perimetry will be performed for VF measurements (Humphrey, 24-2 and 10-2 SITA Standard Program, with fixation losses, false positive and false negative rates, which should be <20%). The main indices of Humphrey perimetry are: Mean Deviation (MD) and Pattern Standard Deviation (PSD) and Mean Sensitivity (MS). The MD establishes the average of the defect obtained in all the points tested, considers the increasing dispersion of sensitivity values with respect to the data obtained in normal subjects based on the eccentricities and therefore can represent an index of the severity of the global damage. PSD indicates the homogeneity of the distribution of the visual field defect and thus provides information on localized damage. MS is the average of the sensitivity values measured at each probed point.

5.5.2. Electrophysiological Evaluations

a) Pattern electroretinogram (PERG)

The PERG shows the bioelectric activity of the innermost layers of the retina (ganglion cells, their fibres). PERG response is characterised by a series of waves with three successive peaks, with polarity negative, positive and negative respectively. In normal people, these peaks have the following implicit times: 35, 50 and 95 msec (N35, P50 and N95). An increase in the N35, P50 and N95 times and a decrease in amplitude N35-P50 and P50-N95 was found in glaucoma patients. These abnormalities in PERG are significantly related to visual field defects and to a reduction in the thickness of the layer of nerve fibres.

Also, PERG has shown a high clinical capacity (sensitivity: 100%, specificity: 100%) to detect malfunctions of the ganglion cells in glaucoma patients (43).

b) Visual evoked potentials (PEV)

VEPs reflect the bioelectric activity of the visual cortex in response to visual stimulation and thus evaluate the function of the visual pathway as a whole. VEP response is characterised by a series of waves with three successive peaks, with polarity negative, positive and negative respectively. In normal people, these peaks have the following times: 75, 100 and 145 msec (N75, P100 and N145). An increase in the N75, P100 and N145 times and a decrease in amplitude N75- P100 and P100-N145 was found in glaucoma patients. These VEP abnormalities are significantly correlated with visual field defects. Also, VEP has shown a high clinical capacity (sensitivity: 100%, specificity: 100%) to detect a delay in the neural conduction along the visual pathways in patients with glaucoma (43).

Comparing VEP and PERG times allows for the obtaining a neural conduction index in the postretinal visual pathways. In fact, the difference between the VEP P100 and P50 times is known as "Retino-cortical Time (RCT)".

5.5.3. Morphological Evaluation

Optical coherence tomography (OCT)

OCT is a non-invasive imaging technique designed to quantitatively evaluate, in cross section, the macular retinal layers, the peripapillary retinal nerve fiber layer, where the ganglion cell axons reside, and the optic nerve head, in vivo. The most recent generation of OCT available on the market is equipped with Spectral Domain (SD-OCT) technology, characterized by higher axial resolution

and faster scanning speed than the previous Time Domain technology, leading to less susceptibility to artifacts eye movement and improved reproducibility of measurements. Furthermore, with SD-OCT it is possible to obtain the segmentation of the internal retinal layers (ganglion cell layer and internal plexiform layer) from the total macular thickness, thus measuring the layers where the cell bodies and the dendrites of the ganglion cells reside, primarily affected by glaucomatous disease.

5.5.4. Neuroradiological Evaluation

MRI with a diffusion tensor allows you to study the diffusivity of water molecules along the various directions of the axes, in order to calculate the fractional diffusivity, the average, axial and radial diffusivity. With this acquisition technique we will evaluate the microstructural integrity of the thalami in its entirety and of the lateral geniculate ganglion. Furthermore, we will evaluate the structural integrity of the optical sections.

Voxel-based morphometry allows us to analyze the volume of cortical gray matter, white matter and CSF. This technique will be used to verify the presence of variations in neuronal density in the various cortical areas, linked or not to the visual system.

Functional MR at rest is an MRI technique that allows to study the low frequency oscillations of the BOLD signal of the cortical gray related to the “rest” task. The functional assumption is that if the BOLD signal of a certain number of cortical areas fluctuates coherently with each other, then they form a functional resting-state network (RSN). We will use this acquisition technique in order to study the connectivity strength of the various RSNs linked or not to the visual system. In addition, we will use a "seed-based" approach, using the thalamus in its entirety and the NGL as areas of interest in order to verify their functional connectivity with the various cortical networks.

5.6 Efficacy parameters

- 1) For the evaluation of the RCT, the difference of the latency time P100 of the PEV and the latency time P50 of the PERG will be considered.
- 2) For the assessment of the visual field (HFA 24-2 and 10-2), the following will be considered: MS, MD and PSD.
- 3) The following parameters will be recorded for each SD-OCT imaging session:
 - the average thickness of the layer of the peripapillary retinal nerve fibers and the thickness divided by sectors.
 - the average thickness of the neural rim and the thickness divided by sectors
 - the average thickness of the ganglion cell layer and the internal plexiform layer (GCL / IPL) and the thickness divided by sectors
- 4) For each diffusion-weighted MRI acquisition, the following parameters of the thalami and LGN and of the optical tracts will be acquired: fractional anisotropy (FA), average diffusivity (MD, axial (AD) and radial (RD)).
For each acquisition of morphometry based on the voxel, the neuronal density of all cortical areas of the entire brain will be acquired.
For functional MRI at rest, the connectivity strength (Z-score) of all the independent cortical networks (linked to vision and not, independently) will be analyzed, as well as the degree of functional

connectivity between the thalami and the LGN and RSNs detected in the previous independent analysis.

6. ASSIGNMENT AND MASKING

Patients with OAG will be selected from a large cohort of already known diseases and followed at our facility for at least 12 months.

Only patients who meet the inclusion criteria will be selected. Patients will undergo a baseline screening visit during which conditions corresponding to the inclusion criteria will be assessed and the study will be proposed.

Only after the signing of the informed consent, a single investigator ("enrolling physician"), not involved in the clinical and instrumental evaluations, will decide whether to assign the selected patient to one of two groups: treated-Citicoline or treated-Placebo.

The assignment to one or the other group will take place in sequential order of presentation of the patient (with a 1: 1 probability of joining one or the other group) in order to constitute two homogeneous groups in number.

The aforementioned assignment will not be known to the patient and will not be known to the "enrolling physician".

Consequently, during the entire duration of the study (both at the baseline visit and at the 6 and 12 month visit), all evaluations foreseen by the study will be carried out by investigators who will not know whether the patient being examined belongs to the Citicoline-treated group or treated-Placebo.

7. TREATMENT OF SUBJECTS

The active form of the food for special medical purposes under study will be produced in accordance with the Good Manufacturing Standards, GMP (Good Manufacturing Practice) and labeled according to the applicable regulatory provisions.

7.1 Dosage, posology and route of administration

During the randomized treatment period, patients will take:

- a) Neurotidine ® at a dosage of 10 ml / day.
- b) Placebo at a dosage of 10 ml / day.

7.2 Composition of the treatment in use

The food intended for special medical purposes Neurotidine Ofta® under study is produced by Omikron Italia, srl.

Each bottle of Neurotidine will contain:

water; fructose; Citicoline (500 mg per 10 ml); acidity regulators: sodium citrate, sodium hydroxide; preservative: potassium sorbate; dye: riboflavine.

Each bottle of Placebo, the solution of which will be indistinguishable from the active product in terms of appearance and flavor, will contain:

water; fructose; acidity regulators: sodium citrate, sodium hydroxide; preservative: potassium sorbate; dye: riboflavin.

7.3 Packing of integrator supplement

The samples of Neurotidine® or of Placebo required for the conducting of the study will be provided free of charge by Omikron Italy.

7.4 Preservation method for Neurotidine® or Placebo

The Investigator must store the samples of Neurotidine® or of Placebo at appropriate temperature and humidity conditions as indicated on the label, in the Institution's internal Pharmacy or in his/her department in a locked room, accessible only to persons authorised to withdraw the samples.

7.5 Drug accountability

The Investigator and the Pharmacy will be responsible for receiving, storing and consigning the food supplement and the Placebo to patients; the Investigator will keep an inventory of the amounts stored and of those returned by individual patients.

7.6 Preservation of materials

The vials of Neurotidine® or of Placebo will be sent to the Pharmacy of the Study Centre and must be stored at the Pharmacy of the Study Centre in a locked area, with access limited to the personnel involved only, out of reach of children, at appropriate temperature and humidity conditions and kept in the boxes provided until used to protect it from exposure to light.

7.7 Concomitant Pharmacological Treatments

Information on concomitant pharmacological treatments includes information on the treatments administered at the time of being included in the study (recorded in the “Ongoing systemic therapies” section of the CRF). Any pharmacological treatment taken for diseases unrelated to that of the study and considered necessary for the patient’s health which does not interfere with the food supplement of the study, may be administered as deemed fit by the Investigator and the GP. All treatments should be recorded in the CRF, indicating the dosage and date of administration as required. In addition, if, due to the onset of symptoms and/or signs after commencing administration of the food supplement, the administration of any type of medication should become necessary, this should be reported in the “Ongoing systemic therapies” section of the CRF.

7.8 Admitted Therapies

During the experimental treatment period, any medications considered essential for the treatment of any concomitant diseases may be administered. Any changes in dosage and/or new concomitant therapies will only be introduced if strictly necessary, and must be reported on the Patient's Medical Record and the study CRF.

7.9 Not-admitted therapies

The administration of medications that may interfere with the assessment of oral Citicoline supplements or which could alter the evaluation of efficacy parameters, and in particular medications with potential effects on retinal or macular function or nerve conduction along the

optic pathways, such as:

- cerebral vasoactives
- neurotrophics
- lutein, zeaxanthin, retinals
- docosahexaenoic acid
- ubiquinone and/or its derivatives, may not be administered.

Any previous treatment with Ubiquinone, L-Carnitine, Citicoline and/or its derivatives in other formulations and/or dosages must have been discontinued at least 6 months prior to inclusion in the study.

7.10 Compliance with treatment

The importance of regularly assuming what is assigned by the "recruiting physician" (Neurotidine® or Placebo) must be emphasized by the Investigator to the patient, who, based on the signature of the informed consent, must also be instructed to return, during the follow-up visits following the delivery date, according to the timing of the study, the unused and / or surplus samples (bottles).

In this way, the Investigator will be able to fill in, both during the control visits and at the end of the trial, the section of the CRF in which compliance with the prescription is recorded, calculate the compliance with the treatment and provide for the conservation of the material returned in a place accessible only to authorized persons.

At T2 and T3 compliance will be assessed by counting the quantity of product returned by the patient because it is not used and calculating the ratio between the number of quantities taken and the quantity that should have been taken according to the dosage schedule provided by the protocol.

Based on compliance, all patients who have taken at least 80% of the prescribed dosage regimen will be considered compliant with the treatment.

7.11 Suspension/interruption of treatment

The food supplement may be discontinued spontaneously by the patient at any time he/she deems appropriate or upon decision of the Investigator (the patient will be considered "drop-out") should his/her clinical conditions require. Any discontinuation must be fully documented in the CRF by the Investigator.

Treatment may be discontinued prematurely for the following reasons:

- refusal of the patient to continue treatment;
- the occurrence of an Incident that may interfere with the patient's assessment or cause the continuation of the study to be considered inappropriate;
- logistical variations that make it impossible for the patient to participate in the study.

It will be the Investigator's responsibility to follow-up patients after discontinuation for an appropriate period of time (30 days) to assess their clinical conditions and/or verify the occurrence of Incidents even after the end of the trial therapy.

It is also recommended that these patients carry out the check-ups envisaged for the end of the study, since they will equally be considered for the intention-to-treat analysis.

For each of the patients who drops out of the trial, all available documentation will however be collected, where clinically possible, until they leave the study.

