9. STATISTICAL ANALYSIS

9.1 Sample size

As already highlighted, the main measure on which we relied for the calculation of the sample size is the RCT.

Our aim is to evaluate the value of the RCT parameter in the group treated with Neurotidine®, compared to that of the group treated with placebo.

We consider the following RCT values: at baseline 70.21 ± 9.12 ms and at the end of treatment 63.3 ± 8.15 ms (19), with an α error of 5% and a power of 80%.

We obtain 27 participants to which we add a drop-out equal to 10%, so the final value is 30 for each group.

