9.2 General methodology

The data of each group, obtained from the PEV, PERG, CV, OCT and RM measurements will be represented by their mean and standard deviation, after having verified their normal distribution by means of the Anderson-Darling and Kolmogorov-Smirnov tests.

For each group, any variations in the measurements indicated above will be evaluated by means of a t-test for paired data.

Furthermore, the parameters of the electrophysiological, morphological and MRI measurements related to the two groups will be compared pre and post treatment, by means of ANOVA with correction of multiple comparisons based on Tukey's method.

The functional electrophysiological parameters (PEV and PERG) will be correlated by Pearson's test with the morphological OCT ones.

Finally, the possible relationship between the PEV, PERG and functional RM parameters of connection of the networks will be assessed using Pearson's test.

This analysis will be repeated respectively between the PEV and PERG parameters and the RM parameters in diffusion for each area indicated in paragraph 5.6.

The p-value of less than 5% is considered significant for any previously exposed test.

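### Section 7.11 promises intention-to-treat but only recommends outcome tests after the supplement is stopped, so the 12-month RCT values that the analysis needs are not secured

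*Protocol*

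**What the plan says.** Section 7.11 (Suspension/interruption of treatment) contains the protocol's only mention of intention-to-treat. Of patients who stop the supplement it says "It is also recommended that these patients carry out the check-ups envisaged for the end of the study", and gives the reason: "since they will equally be considered for the intention-to-treat analysis".

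The same section sets three other rules.

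- The investigator's stated duty after stopping is to "follow-up patients after discontinuation for an appropriate period of time (30 days"), in order to check clinical condition and Incidents. The efficacy tests are not part of that duty.
- For patients who drop out of the trial, "all available documentation will however be collected, where clinically possible, until they leave the study".
- The drop-out label appears in the sentence on discontinuing the supplement, and some of the listed reasons for ending treatment concern taking part in the study.

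Section 9.1 reaches 27 per group, "to which we add a drop-out equal to 10" per cent, and so plans 30.

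Section 9.2 names the tests. Within groups: "For each group, any variations in the measurements indicated above will be evaluated by means of a t-test for paired data". Between groups, the parameters "will be compared pre and post treatment, by means of ANOVA with correction of multiple comparisons based on Tukey's method". It names no analysis population.

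Sections 5.2 to 5.4 schedule PERG and VEP at T0, T1, T2 (6 months) and T3 (12 months). Section 5.6 defines RCT from those two recordings.

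**The concern.** An intention-to-treat comparison needs the outcome of each randomised patient, whether or not the supplement was continued. Section 7.11 recognises this, since it gives intention-to-treat as the reason for the end-of-study tests, but it leaves those tests to voluntary attendance. It also does not say whether they take place when the patient stops or at month 12. A recording made soon after an early stop is not a 12-month value.

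Patients who stop because they see no benefit or do not tolerate the product need not resemble those who continue. If their RCT is missing, the between-group difference can move in favour of either arm. No analysis plan can recover an RCT that was never recorded, so this has to be settled in the protocol.

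**Working it through.** **1. The rules side by side**

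- Promise (7.11): patients who stop are in the intention-to-treat analysis.
- Required after stopping (7.11): 30 days of clinical and Incident follow-up.
- Recommended only (7.11): the end-of-study check-ups, which are where the post-treatment RCT would come from.
- Analysis (9.2): a paired t-test needs a pre and a post value for each patient. A pre/post ANOVA on observed values likewise has no post value for a patient who does not attend.

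A patient who stops and attends T3 can be analysed as promised. One who stops and does not attend has broken no rule and has no T3 value.

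**2. The protocol's sample size**

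Inputs from 9.1: RCT 70.21 (SD 9.12) ms at baseline and 63.3 (SD 8.15) ms at the end of treatment, alpha 5% (two-sided assumed), power 80%.

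- Difference = 70.21 − 63.3 = 6.91 ms.
- Pooled SD = √((9.12² + 8.15²)/2) = √74.80 = 8.65 ms.
- n = 2 × (1.960 + 0.842)² × 74.80 / 6.91² = 24.6, so 25 per group. The t-test version gives 26.
- The stated 27 is within 2 of this, and 27/0.9 = 30 matches.

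At the planned rate, about 3 of 30 patients per arm are affected.

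**3. Moderate selection**

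If a share f of an arm stops and has no T3 value, and stoppers differ from the remaining patients by d, the mean of those observed differs from the mean of the whole arm by f × d. The protocol gives no d, so 3 ms and 6.91 ms (the whole planned effect) are assumed.

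- f = 10%: 0.1 × 3 = 0.3 ms, and 0.1 × 6.91 = 0.7 ms.
- f = 20%: 0.2 × 3 = 0.6 ms, and 0.2 × 6.91 = 1.4 ms.

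**4. Extreme selection**

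Suppose exactly the least-improved 10% of one arm are lost, none attend T3, nothing offsets this in the other arm, and changes are normally distributed. The shift is SD of change × φ(z)/(1 − f), with φ(z) = 0.1755 at f = 0.10. The SD of change depends on the correlation between the two time points, which the protocol does not give.

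- Correlation 0.5: SD = √(9.12² + 8.15² − 9.12 × 8.15) = 8.68 ms. Shift = 8.68 × 0.1755/0.9 = 1.7 ms, or 24% of 6.91 ms.
- Correlation 0.8: about 1.1 ms. Correlation 0.2: about 2.1 ms.

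**5. What full follow-up does to the effect and the power**

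Take 6.91 ms as the between-arm difference, as 9.1 does. Power (normal approximation) = Φ(difference/(8.65 × √(2/n)) − 1.96).

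| Case | Difference | Power |
|---|---|---|
| 27 per arm observed | 6.91 ms | 83.5% |
| 30 per arm, 10% stop citicoline and lose all effect | 6.91 × 0.9 = 6.22 ms | 79.5% |
| 30 per arm, 10% stop and keep half the effect | 6.91 × 0.95 = 6.56 ms | 83.6% |
| 30 per arm, 20% stop and lose all effect | 6.91 × 0.8 = 5.53 ms | 69.7% |

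**The case against.** The best defence is that 7.11 points the right way. It excludes nobody who stops, asks them to attend the end-of-study tests, and gives intention-to-treat as the reason. The sentence on collecting data until departure can be read as covering only patients who leave the trial, where collection naturally ends. The drop-out label follows the clause on the investigator's decision, so it may not reach patients who stop of their own accord. The 10% in 9.1 is routine inflation and defines no analysis set. The choice of population, the handling of missing values and the use of T2 may be settled in an analysis plan that is not shown here.

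Much of this stands, and it rules out several stronger readings.

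- A reader might infer that the analysis becomes one of completers only. The protocol does not say so, and patients who stop and attend T3 are kept.
- A reader might infer that the intention-to-treat estimate cannot be produced. The text supports only that it is not guaranteed.
- A reader might infer that the 6-month RCT goes unused. Section 9.2 says neither that it is used nor that it is not.
- A reader might take 1.7 ms as the expected bias. It is a worst case. Section 7.11 also allows for practical obstacles to taking part, which need not be related to outcome.

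The defence does not remove the central gap. The tests are recommended and not required, and that recommendation follows a list of reasons that includes the patient's own refusal, so it covers both kinds of stopper.

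**Conclusion.** The point holds as a gap in data collection. Section 7.11 promises an analysis whose outcome data depend on voluntary attendance, and its wording does not clearly separate stopping the supplement from leaving the study. The comparisons in 9.2 are therefore at risk of reducing to patients with an observed T3 value.

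The size and direction of any bias are unknown. At 10% stopping in one arm, moderate assumptions give 0.3 to 0.7 ms. The upper bound is about 1.7 ms at an assumed correlation of 0.5 (1.1 to 2.1 ms for correlations of 0.8 to 0.2). The planned difference is 6.91 ms. Loss of power is not the main issue, since 27 observed per arm still gives 83.5%. This is a worthwhile, inexpensive improvement. It does not show that the trial's result would be invalid.

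**What to change.** - **Section 7.11:** define stopping the supplement and withdrawing from the study as separate events. Require the PERG and VEP recordings (RCT) at T2 and T3, at their scheduled times, for every randomised patient unless consent is withdrawn.
- **Section 9.2:** state that the primary between-group comparison includes all randomised patients in the group to which they were assigned. A repeated-measures model using T1, T2 and T3 is one suitable option, because patients with only a T2 value after baseline would still contribute. It may be set in the analysis plan.

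The cost is a few sentences and no new visits. About 3 patients per arm at the planned rate are asked to attend visits that are now optional for them. The rules on when the supplement may be stopped are not affected.

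The downside is that the all-randomised effect may be somewhat diluted: 6.2 against 6.9 ms if 10% stop and lose all effect, with power at about the planned 80%. If 20% stopped and lost all effect, power would fall to about 70%.
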